8.5. Pharmacodynamics

Pharmacodynamic parameters are not evaluated in this study.

8.6. Genetics

A genetic sample is not required in this study.

8.7. Biomarkers

Biomarkers are not evaluated in this study.

9. STATISTICAL CONSIDERATIONS

9.1. Statistical Hypotheses

No formal statistical hypotheses are to be tested.

9.2. Sample Size Determination

9.2.1 Sample Size Assumptions

Parts 1 and 2

Sample size is based on feasibility. No formal calculation of power or sample size (i.e., sample size sensitivity or robustness) for Parts 1 and 2 of the study has been performed. A sample size of approximately 9 participants (6 active: 3 placebo) per dose-cohort should be sufficient to provide useful estimates of both inter- and intra-participant variability for VH3739937, PK parameters, and initial safety assessment.

Sample size re-estimation is not planned.

Data will be reviewed by the DEC prior to each dose escalation; no other interim analysis is planned.

Part 3

This is the first study which will evaluate the pharmacokinetic properties of VH3739937 in humans following oral administration of suspension and tablet formulations. Results from previous PK studies for GSK3640254 (a similar compound to VH3739937), and observed preliminary data from Part 1 of the study suggest that 25% is a conservative estimate for percent within subject coefficient of variation (%CVw) of Cmax and AUC(0-t) and will therefore be used to assess the precision (i.e. half width of the 90% confidence interval on the log and ratio scale) potential sample sizes of this three period crossover RBA/FE study. Assuming a within participant coefficient of variation of 25% and a sample size of 12 participants, it is estimated that the half width of the 90% confidence interval for the formulation difference on the log-scale will be within 0.173 of the point estimate (assumed to be 1.0). If the point estimate of the ratio of geometric means is assumed to be 1.0, then the 90% confidence interval will be approximately (0.841, 1.189) on the original scale.

Since tablet formulation and amount of food consumed may change the exposure to VH3739937, a range of point estimates for true ratio of 0.9, 1.0, and 1.1 were used in combination with sample sizes ranging from 12 to 18. The resulting estimated 90% confidence intervals are shown in [Table 13](#) below.

Table 13 90% Confidence Intervals for RBA/FE of VH3739937

n	%CVw	Point Estimate	90% CI
12	25	0.9	(0.757, 1.070)
12	25	1	(0.841, 1.189)
12	25	1.1	(0.925, 1.308)
15	25	0.9	(0.772, 1.049)
15	25	1	(0.858, 1.166)
15	25	1.1	(0.944, 1.282)
18	25	0.9	(0.783, 1.034)
18	25	1	(0.870, 1.149)
18	25	1.1	(0.957, 1.264)

9.2.2 Sample Size Sensitivity

To assess the sensitivity of sample size to within participant variability of the PK parameters, point estimates and 90% confidence intervals for a sample size of 12 participants with a true ratio of 1.0 were calculated for %CVw values ranging from 15% to 35% were also considered and shown in [Table 14](#) below.

Table 14 Sample Size Sensitivity for RBA/FE of VH3739937

N	%CVw	Point Estimate	90% CI
12	15	0.9	(0.810, 1.000)
12	25	0.9	(0.757, 1.070)
12	35	0.9	(0.708, 1.143)
12	15	1	(0.900, 1.111)

N	%CVw	Point Estimate	90% CI
12	25	1	(0.841, 1.189)
12	35	1	(0.787, 1.270)

Approximately 18 participants will be enrolled to ensure that approximately 12 evaluable participants complete the study.

9.3. Populations for Analyses

For purposes of analysis, the following populations are defined:

Population	Description
Enrolled	All participants who sign the ICF
Safety	All participants who received at least 1 dose of study intervention. Participants will be analyzed according to the intervention they received.
Pharmacokinetic Concentration	The PK Concentration Population will include all participants who undergo plasma PK sampling and have evaluable PK assay results. This population will be used for the concentration listing.
Pharmacokinetic Parameter	The PK Parameter Population will include all participants who undergo plasma PK sampling and have evaluable PK parameters estimated. This population will be used for PK parameter listing, plotting of the concentration-time data and PK parameter summary.

9.4. Statistical Analyses

9.4.1. Safety Analyses

All safety analyses will be performed on the Safety Population and details will be provided in the Reporting and Analysis Plan (RAP).

Endpoint	Statistical Analysis Methods
Primary	Safety data will be presented in tabular and or graphic format and summarized descriptively accordingly to GSK's Integrated Data Standards Library (IDSL) standards
Exploratory	Will be described in the reporting and analysis plan

AEs will be tabulated using Medical Dictionary for Regulatory Activities (MedDRA) preferred terms. The number and percentage of participants experiencing each specific AEs (All AEs, Grade 2 or higher, and SAEs) will be tabulated by severity and by relationship to study product. For the calculations in these tables, each participant's AEs will be counted once under the maximum severity or the strongest relationship to study product. AEs leading to withdrawal will also be summarized by treatment.

9.4.2. Other Analyses

PK and pharmacodynamic exploratory analyses will be described in the reporting and analysis plan. The population PK analysis and pharmacodynamic analyses will be presented separately from the main clinical study report (CSR).

Additionally, special statistical and data analysis considerations may be warranted in the event that the COVID-19 or related epidemics or natural disasters may affect the study and data integrity. To the extent possible, these will be described in the study RAP.

9.4.3. Pharmacokinetic Analyses

Plasma VH3739937 concentration-time data will be analyzed by noncompartmental methods using WinNonlin Professional 5.2 or higher, Phoenix (Pharsight Corporation) or comparable software. The various analyses will be conducted as permitted by data available. Individual plasma PK parameters for each participant and dosing group will be determined, including:

- Part 1 (single dose): $AUC_{(0-24)}$, $AUC_{(0-\tau)}$, $AUC_{(0-\infty)}$, C_{max} , C_{24} , t_{max} , t_{lag} , $t_{1/2}$, C_{last} , t_{last} , CL/F .
- Part 2 (repeated once daily [QD] dose):
 - Day 1: $AUC_{(0-24)}$, C_{max} , C_{24} , t_{max} , t_{lag}
 - Day 14 (Cohort 3 and 4): $AUC_{(0-\tau)}$, C_{max} , $C\tau$, t_{max} , $t_{1/2}$, and CL/F
 - Day 18 (Cohort 5): $AUC_{(0-t)}$, C_{max} , Ct , t_{max} , $t_{1/2}$, and CL/F
- Part 2 (repeated once weekly [QW] dose):
 - Day 1 (Cohort 6): $AUC_{(0-168)}$, C_{max} , C_{168} , t_{max} , t_{lag}
 - Day 15 (Cohort 6): $AUC_{(0-t)}$, C_{max} , Ct , t_{max} , $t_{1/2}$, and CL/F
- Part 3 (Single Dose Relative Bioavailability):
 - $AUC_{(0-24)}$, $AUC_{(0-\infty)}$, C_{max} , C_{24} , t_{max} , t_{lag} , $t_{1/2}$, C_{last} , t_{last} , CL/F

9.4.4. Statistical Analysis of Pharmacokinetic Data

- Statistical analyses of the pharmacokinetic parameter data will be the responsibility of Clinical Statistics, GSK.
- Plasma VH3739937 concentrations and PK data will be summarized by treatment and listed by participant. Unless stated otherwise, descriptive summaries will include number (n), mean, standard deviation (SD), coefficient of variation (%CV), median, minimum, and maximum for continuous variables, n and percent (%) for categorical variables, and geometric mean, 95% confidence interval (CI), and the between-participant CV (%CVb) for the log-transformed PK parameters.
- Dose proportionality of selected single and repeated dose PK parameters will be assessed by the power model.

- Accumulation will also be:
 - Predicting from single dose data (Part 1) based on AUC as follows: $R_p = \frac{AUC(0-\infty)}{AUC(0-\tau)}$ day 1 / $AUC(0-\tau)$ day 1
 - Evaluated for each treatment by determining the ratio of Day 14 for cohort 3 and 4, Day 18 for cohort 5, and Day 15 for cohort 6 (Part 2) to Day 1 $AUC(0-\tau)$ ($R(AUC(0-\tau))$), C_{max} ($R(C_{max})$), and C_{τ} ($R(C_{\tau})$). C_{24} on Day 1 will be taken as the C_{τ} on that day.
- Assessment of steady-state VH3739937 concentrations will be assessed in Part 2 by estimating the slope of pre-dose concentrations on Days 2-14 for Cohorts 3 and 4, Days 2-18 for Cohort 5 and Days 2-15 for Cohort 6. The final assessment of the slope will be determined by at least the last 3 pre-dose concentrations.
- **Part 3**
For the assessment of relative bioavailability of formulation and food effect (if conducted), the \log_e -transformed PK parameters will be analysed as data permits using separate mixed effect models with a fixed effect term for fed vs. fasted and tablet vs PiB. Participant will be treated as a random effect in each model. Point estimates and their associated 90% CIs will be calculated for the difference in $AUC_{(0-24)}$, $AUC_{(0-\infty)}$, and C_{max} for the tablet vs PiB and fed vs fasted comparisons. The point estimates and their associated 90% CIs will then be back-transformed to provide point estimates and 90% CIs for the ratios of tablet vs PiB and fed vs fasted in PK parameter values on the original scale.
- Full details of the statistical analysis of PK data will be described in the RAP.

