Vital signs		X	X	X (Days 2, 4, and 6)	X	X (Days 10, 12 and 14)	X	X		X		X		Vital signs to be performed pre-dose. Temperature will be monitored every day during study participation. For further detail, see Section 8.1.2
12-lead safety ECGs		X	X	X	X	X	X	X	X	X	X	X		ECG should be performed pre-dose on dosing days. ECG timepoints may be reduced in subsequent dosing groups. For further detail, see Section 8.1.4
Testing for SARS CoV-2	X			X (Day 7)		X (Day 14)						X		An additional SARS-CoV-2 test will be performed approximately one week prior to admission to the unit. Weekly SARS-CoV-2 testing is required while in the unit (Days 7, 14) and on discharge (Day 20). An approved molecular

Procedure	Pre-Treatment Days		Week 1		Week 2		Week 3		In House Post Treatment Days					Notes
	Treatment Days		Treatment Days		Treatment Days									
	-2	-1	1	2, 3, 4, 5, 6, 7	8	9, 10, 11, 12, 13, 14	15	16 24h	17 48h	18 72h	19 96h	20 120h		
														Hours (h) relate to PK sampling post last dose
Drug/alcohol/nicotine screen	X													test (PCR) will be used. For further detail see Appendix 7 and Section 8.1.3
Haematology/Chemistry/Urine tests		X	X	X (Days 2, 4 and 6)	X	X (Days 9, 11 and 13)	X		X		X	X		For further detail, see Appendix 2
Pregnancy Test	X													Female participants only. For further detail see Appendix 2
VH3739937 Dose Administration			X		X		X							Weekly oral dose on Days 1, 8 and 15. Randomization to occur on Day 1 prior to dosing. For meal instructions prior to dose, see Section 5.3.1
Meals	Per site usual practice													
Plasma PK Sampling			X	X	X	X	X	X	X	X	X	X		2mL of blood will be collected at pre-dose (within 15 mins prior to dosing) and 1, 2, 3, 4, 5, 6, 7, 8, 9, 10, 12, and 16 h on Days 1, 8 and Day 15. The 24 h post day 1 dose collection on Days 2, 9 and 15 will be taken at post-dose collection timepoint. At all other timepoints on non-dosing days (Days 3, 4, 5, 6, 7, 10, 11, 12, 13, 14, 16, 17, 18, 19, 20), samples will be drawn at the post-dose

Procedure	Pre-Treatment Days		Week 1		Week 2		Week 3		In House Post Treatment Days					Notes		
	Treatment Days		Treatment Days		Treatment Days											
	-2	-1	1	2, 3, 4, 5, 6, 7	8	9, 10, 11, 12, 13, 14	15	16 24h	17 48h	18 72h	19 96h	20 120h				
Urine PK			X	X (Day 2, end of 24hr collection from Day 1)	X	X (Day 9, end of 24hr collection from Day 8)	X	X (Day 16, end of 24hr collection from Day 15)						Hours (h) relate to PK sampling post last dose		

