2. SUMMARY OF KEY PROTOCOL INFORMATION

2.1. Changes to the Protocol Defined Statistical Analysis Plan

There were no changes or deviations to the originally planned statistical analysis specified in most recent version of the protocol Amendment 2 (212548/02) [(Dated: 16-Mar-2021)] which introduced Part 3 (relative bioavailability and food effect).

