8.1.5.1.3. Assessment of Steady State

For Part 2 cohorts 3 and 4, steady-state VH3739937 concentrations will be assessed by estimating the slope of concentrations on pre-dose assessments on Days 2-14 (Part 2 cohort 3 and 4) and the day 15 24-hr post-dose (relative to dosing on day 14). For Part 2 cohort 5, steady state VH37339937 concentrations will be assessed by estimating the slope of the concentrations of pre-dose assessments on Days 2-18 and the day 19 24-hr post-dose (relative to dosing on day 18).

To determine when steady state is achieved the separate mixed effects linear regression models will be estimated for each treatment and each subset of days. The first subset of days will include all $C\tau$ values for days 2-15. Then the value from the earliest timepoint will be dropped and the analysis re-run. Earlier days will be iteratively dropped (e.g. Days 2-15, then Days 3-15, then Days 4-15, etc.) until only 3 dosing days, and the 24-hr post final dose assessment, remain. The final assessment of the slope will be determined by at least the last 3 pre-dose concentrations and the concentration 24 hours post last dose.

Endpoint / Variables

 $C\tau$ Day (2-15) for Part 2 Cohort 3 and 4 $C\tau$ Day (2-19) for Part 2 Cohort 5
Model Specification

 In the model for Part 2 Cohort 3 and 4, $C\tau$ Day (2-15) will be the dependent variable, day will be included as a fixed effect, and participant will be included as a random effect In the model for Part 2 Cohort 5, $C\tau$ Day (2-19) will be the dependent variable, day will be included as a fixed effect, and participant will be included as a random effect
Model Checking & Diagnostics

 Normality assumptions underlying the model used for analysis will be examined by obtaining a normal probability plot of the residuals and a plot of the residuals versus the fitted values (i.e. checking the normality assumption and constant variance assumption)

of the model respectively) to gain confidence that the model assumptions are reasonable.
 
 • If there are any departures from the distributional assumptions, alternative models will be explored using appropriate transformed data.
Model Results Presentation

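### Protocol 9.4.4 applies daily-dosing rules to weekly Cohort 6 (a three-point trough slope with two troughs, and C24 as the Day 1 trough); the SAP largely avoids this but does not say so

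*Protocol*

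**What the plan says.** **Protocol 9.4.4.**
- Accumulation is the ratio of the last dosing day, "Day 18 for cohort 5, and Day 15 for cohort 6 (Part 2) to Day 1", for AUC(0-τ), Cmax and Cτ. The next sentence says that C24 "on Day 1 will be taken as the" Cτ for that day. It is not limited to the daily cohorts.
- Steady state is assessed by a slope through the troughs. For the two later cohorts the window is given as "Days 2-18 for Cohort 5 and Days 2-15 for Cohort 6"; the two earlier ones stop at Day 14. A minimum number of values is then set for every cohort alike: "The final assessment of the slope will be determined by at least the last 3 pre-dose concentrations".
- Full details are left to the reporting and analysis plan, that is, the SAP.

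**Protocol 1.2, Table 5 (Cohort 6).** Dosing is described as "Weekly oral dose on Days 1, 8 and 15". The pre-dose sample and the serial samples run up to 12 "and 16 h on Days 1, 8 and Day 15". On non-dosing days samples are taken at the post-dose clock time. After the third dose the samples go from 120 h (Day 20) to 192 h (Day 23).

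**Protocol 3 and 9.4.3.** The time-to-steady-state endpoint lists Cohorts 3, 4 and 5 only. For Cohort 6 on Day 1 the listed parameters include C168 and AUC(0-168), not C24.

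**SAP.**
- 8.1.5.1.2 places the C24 definition in the paragraph on Cohorts 3 to 5, then treats Cohort 6 separately with τ = 168 h.
- 8.1.5.1.3 begins "For Part 2 cohorts 3 and 4, steady-state VH3739937 concentrations will be assessed by estimating the slope" and adds Cohort 5. Cohort 6 does not appear there, nor in the instructions for Table 4.6.
- 2.1 states: "There were no changes or deviations to the originally planned statistical analysis".

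**The concern.** Both rules in Protocol 9.4.4 suit a 24 h dosing interval. For a weekly regimen, the slope rule asks for more troughs than the schedule provides. The C24 rule compares a concentration at the end of a 168 h interval with one taken about a seventh of the way through it. An analyst working from the protocol alone could not run the first rule. The second would give a trough ratio below 1, against the protocol's own expectation of 1.3-fold weekly accumulation.

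The SAP does something different and more sensible, but a reader of SAP 2.1 is told that nothing differs from Amendment 2. What is at stake is traceability, and one secondary parameter, R(Cτ), in Cohort 6.

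**Working it through.** **1. Pre-dose samples available for the slope** (Protocol 1.2, Tables 3 to 5)

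| Cohort | Window | Pre-dose sample days | Count |
|---|---|---|---|
| 3 and 4 | Days 2-14 | 2, 3, 4, 6, 8, 10, 11, 12, 13, 14 | 10 |
| 5 | Days 2-18 | 2, 3, 4, 6, 8, 10, 12, 14, 15, 16, 17, 18 | 12 |
| 6 | Days 2-15 | 8, 15 | 2 |

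The minimum of three is met in the daily cohorts and cannot be met in Cohort 6. The Day 1 pre-dose sample is outside the window and precedes any drug.

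**2. The protocol's own accumulation figures.** Inputs: half-life about 90 h (Protocol 4.1) and a linear one-compartment model (Protocol 2.2.1). k = ln 2 / 90 = 0.00770 per h. Steady-state accumulation is 1 / (1 − exp(−kτ)).
- Daily: exp(−24k) = 0.831, so 1 / 0.169 = 5.93. Stated: about 6.
- Weekly: q = exp(−168k) = 0.274, so 1 / 0.726 = 1.38. Stated: 1.3, close for a rounded figure; exactly 1.3 needs a half-life of about 79 h.

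**3. R(Cτ) for Cohort 6 after the third dose** (post-absorption)
- Three-dose factor: 1 + q + q² = 1 + 0.274 + 0.075 = 1.349.
- Day 1 trough taken as C168: R(Cτ) = 1.35.
- Day 1 trough taken as C24: C168/C24 after one dose = exp(−144k) = 0.330, so R(Cτ) = 1.349 × 0.330 = 0.445. The true ratio is understated about 3-fold (1 / 0.330 = 3.03).
- First-order absorption at assumed rates of 0.2, 0.5 and 1.0 per h gives 0.450, 0.445 and 0.445 with C24, and 1.349 each time with C168.
- Assumed half-life range of 70 to 110 h: 0.29 to 0.59 with C24; 1.23 to 1.47 with C168.

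**4. The missing 168 h value after dose 3.** R(Cτ) needs a concentration on Day 22, which is not sampled. SAP 8.1.5.1.2 predicts it with a linear model from the other post-dose times. The footnote to Table 4.8 (SAP 13.10.6) replaces it with the 192 h sample. The second method lowers the ratio by a further 24 h of decline: 1.349 × 0.831 = 1.12 instead of 1.35. At 70 h it is 1.225 × 0.788 = 0.97; at 110 h, 1.467 × 0.860 = 1.26.

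**5. What two observed troughs can show.** C168 after dose 2 over C168 after dose 1 is expected to be 1 + q = 1.27. Both values are already derived (SAP 8.1.2, Cohort 6 Days 1 and 8).

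**The case against.** The strongest reply is that the SAP governs the analysis and has already put this right. Protocol 9.4.4 defers to it, C24 is confined there to the daily cohorts, and Cτ is defined generally as the trough at the end of the dosing interval. With τ = 168 h, C168 follows for Cohort 6 by implication. Leaving Cohort 6 out of the slope also agrees with Protocol Section 3, so the protocol contradicts itself and the SAP followed one side. All of this stands. What remains is that Day 1 Cτ = C168 is never stated for Cohort 6, and that SAP 2.1 is inaccurate against 9.4.4.

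Three stronger readings are tempting, and the documents do not support them.

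- *A reader might infer that the study will report weekly accumulation below 1 because of the C24 rule.* That needs 9.4.4 to be followed literally against the SAP. Even then only R(Cτ) is affected.
- *A reader might infer that the SAP leaves Cohort 6 with no look at steady state.* No formal slope remains, but no listed endpoint calls for one. Figure 4.11 plots all Cohort 6 trough points, Figures 4.18 to 4.20 show full profiles, C168 is summarised after doses 1 and 2, and accumulation is estimated.
- *A reader might infer a slope of the wrong sign*, since consecutive daily samples late in a week would fall to about 83% of the day before. But 9.4.4 specifies pre-dose concentrations, and the non-dosing-day samples are not pre-dose. The rule cannot be met; it does not yield a negative slope.

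**Conclusion.** The two rules in Protocol 9.4.4 are wrong as written for Cohort 6: two troughs against a minimum of three, and a Day 1 trough that would put R(Cτ) at about 0.45 instead of about 1.35. Those ratios rest on a one-compartment model and a 90 h half-life, and describe only a literal reading of 9.4.4. The SAP largely avoids the error. Its own shortcomings are the unstated Day 1 definition, the inaccurate declaration in 2.1, and the two methods for the unsampled 168 h value (about 1.12 with the 192 h sample, against 1.35). That last conflict is live in the current SAP and affects the same parameter.

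Severity is minor: secondary, estimation-only PK in one cohort with 7 active participants, and no hypothesis is tested.

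**What to change.** 1. In Protocol 9.4.4, limit the slope and the C24 sentence to Cohorts 3 to 5. If the protocol is not to be amended, record in SAP 2.1 that the SAP departs from 9.4.4 on both points for Cohort 6 and follows Protocol Section 3 on the slope.
2. In SAP 8.1.5.1.2, state that Day 1 Cτ for Cohort 6 is C168.
3. Choose one method for the 168 h concentration after dose 3 and use it in both SAP 8.1.5.1.2 and the Table 4.8 footnote. If the model prediction is kept, name the samples and the scale of the fit. If the 192 h sample is kept, say that it biases the ratio downward.
4. Optionally, report the observed C168 ratio of dose 2 to dose 1 for Cohort 6 (expected about 1.27) as a descriptive measure of early accumulation. It uses no imputed value, but it is not evidence that steady state was reached.

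Cost: SAP wording only, with no new samples. Editing Protocol 9.4.4 would be an amendment needing ethics committee approval (Protocol 10.1.1), so recording the departure in SAP 2.1 is the cheaper route and is sufficient.

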9.4.5. Pharmacokinetic/Pharmacodynamic Analyses

- Pharmacokinetics/Pharmacodynamic (PK/PD) analyses will be performed only if the VH3739937 development project is progressing forward. The end point for the potential impact of VH3739937 on cardiac repolarization will be the change-from-baseline QTcF (ΔQTc). A modelling approach will be used to describe the relationship between VH3739937 concentration and QTc data.
- The details of the PK/PD analysis will be described in the RAP or in a separate analysis plan if the analysis is reported separately.

9.5. Interim Analyses

There will be no formal interim analysis; however, all preliminary safety, tolerability, and available pharmacokinetic data will be reviewed internally at the Dose Escalation Committee (ViiV/GSK) prior to each dose escalation or administration and according to the dose escalation charter. Safety data (labs, vital signs, ECG, AEs, SAEs) will be reviewed by the PI/Sub-I and ViiV/GSK study team after completion of each dose level. Dose escalation can only occur after PI/Sub-I and ViiV/GSK study team has found that the safety, PK profiles are supportive to proceed with the evaluation of the next highest dose level.

At each dose, the Bayesian probability of an individual exceeding the Cmax threshold in Part 1 and the Bayesian probability of an individual exceeding the AUC threshold in Part 2 will be calculated and compared with 50%. This will be used to help selection of the next dose together with safety and tolerability data. The Bayesian probability will be based on Whitehead's model shown below [Whitehead, 2001] using non-informative prior for model parameters.

$$y_{ij} = \theta_1 + \theta_2 d_{ij} + s_i + \epsilon_{ij} \quad [1]$$

Where y_{ij} is log-PK of i -th participant to j -th dose, d_{ij} is j -th log-dose administered to i -th participant. θ_1 and θ_2 are population intercept and slope, respectively. s_i is random effect of i -th participant and ϵ_{ij} is random error of i -th participant in j -th dose.

When intra-participant variability cannot be estimated during PK predictions in Part 1 (i.e., early on in the study when there is not sufficient information to estimate intra-participant variability) and for conducting prediction of all doses in Part 2, the same Whitehead's model will be used for Bayesian probability calculations as below.

$$y_i = \theta_1 + \theta_2 d_i + \epsilon_i \quad [2]$$

Where y_i is log-PK of i -th participant, d_i is the log-dose administered to i -th participant. θ_1 and θ_2 are population intercept and slope, respectively and ϵ_i is random error of i -th participant.

Bayesian model Operating Characteristics (OC)

In this part, we want to explore the operating characteristics of the possibility of escalating to the 800 mg dose in the SAD portion of the study. Given different assumptions of with-in and between participant Cmax variability (CV%), and assuming dose proportionality (slope=1), data for 1000 trials were simulated based on Whitehead's model [1]. Each simulated trial contains Cmax values for 6 subjects on treatment for doses ranging from 10 mg to 640 mg in SAD cohort 1 and cohort 2.

For each simulated trial, we fit the mixed effect Bayesian model based on mode [1]. Using the following procedure, we calculated the Bayesian probability of an individual exceeding the Cmax threshold:

10,000 iterations were simulated in the MCMC procedure. In each iteration, we obtained the estimated parameters $\hat{\theta}_1, \hat{\theta}_2, \hat{s}_i$ ($i = 1, 2, \dots, 6$) and $\hat{\sigma}^2$ (the estimated standard deviation of ϵ_{ij}). Based on the estimation, a random sample for each subject, which represented the simulated exposure in the 800 mg dose, was drawn from the distribution $N(\hat{\theta}_1 + \hat{\theta}_2 \times 800 + s_i, \hat{\sigma}^2)$. We counted the number of iterations N with any simulated exposure exceeding the Cmax threshold $\log(21)$. The Bayesian probability was calculated as $1 - \frac{N}{10,000}$.

For each trial, the Bayesian probability of the 800 mg dose exceeding the Cmax threshold of log(21) was calculated and compared with different thresholds (40%, 50% or 60%). Results showed that all simulated trials had a probability less than 40%, 50%, and 60% in situations with high variability (%CVw = 50, %CVb = 50) as well as scenarios with low variability (%CVw = 12.5, %CVb = 25). These results indicate that the probability of escalating to 800 mg in the SAD is high.

Additional simulations were conducted to determine the probability of escalating to 100 mg during the Part 2 of the study (MAD QD dosing). 1000 simulated trials were produced for each value of %CVb (25, 35, and 50), using a predicted 24-hour steady state AUC of 39.8 $\mu\text{g}^*\text{h}/\text{mL}$. More detailed information may be found in the IB Supplement [GlaxoSmithKline Document Number 2021 [RPS_CLIN_004025](#)]. For each trial, the Bayesian probability of the 100 mg MAD QD dose producing an 24 hour steady state AUC above log(96.2) was calculated. This value was compared to potential evidence thresholds of 40%, 50%, and 60%. **Table 15** shows the probability of a simulated trial having a Bayesian predictive probability of exceeding the AUC safety threshold of log(96.2) less than the various threshold values under the chosen values of CVb.

Table 15 Percentage of simulated trials of 100 QD dosing with Bayesian predicted probability of 24hr steady state AUC under safety threshold of log(96.2) across probability thresholds

AUC Variability	Probability Threshold		
	40%	50%	60%
25	0.995	0.999	1
35	0.934	0.967	0.986
50	0.791	0.880	0.927

These results indicate that the probability of escalating to 100 mg during the MAD QD dosing portion of the study is high.

Finally, simulations were performed to assess the probability of any participant having an 24 hour steady state AUC above log(96.2) or a Cmax above log(21) during the weekly MAD dosing portion of the study. It is anticipated that a 500 mg weekly dose will produce a steady state maximum daily AUC of 31.2 $\mu\text{g}^*\text{h}/\text{mL}$. Under this assumption, 1000 simulated trials were produced for each value of %CVb (25, 35, 5). Each simulated trial included 7 participants dosed at 500 mg. No simulated trial produced any participant who had either an AUC above log(96.2) or a Cmax above log (21). Therefore, the probability of a subject exceeding the safety threshold during the weekly dosing portion of the study is low.

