4.3.4. Part 2 (MAD) Starting Dose and Dose Escalation

The initial dose in the MAD (Cohort 3) was approximately equal to the likely minimally effective dose, re-estimated at 25 mg based on the clinical PK data following oral administration of the suspension formulation collected in the early doses of Part 1. Dose escalation in the MAD will not exceed 2-fold between daily dosing cohorts 4 and 5 and will be governed by both safety and MAD PK stopping criteria (see Section 7.1.4 and Section 7.1.5). Based on emerging PK data in Part 1, the once weekly (QW) dosing Cohort 6 will be dosed at 500 mg. Given different assumptions for the between participant AUC variability (%CVb) and the current human PK prediction, the probability of any participant AUC(0- τ) in the MAD above 96.2 $\mu\text{g}/\text{mL}$, the LOAEL exposure in rat, are illustrated in [Table 8](#). Similarly, the probability of any participant AUC(0-24) which cover the maximum exposure in the MAD Cohort 6 above 96.2 $\mu\text{g}/\text{mL}$ is illustrated in [Table 9](#).

Table 8 Probability of any MAD participant (AUC(0- τ) $> 96.2 \mu\text{g}^*\text{h}/\text{mL}$) for potential QD doses

AUC variability	Potential VH3739937 QD MAD Doses		
	25 mg	50 mg	100 mg
25	0	0	<0.001
35	0	0	0.003
50	0	<0.001	0.028

Note: 1, %CVb: between-participant coefficient of variation

Table 9 Probability of any MAD participant (AUC(0- τ) >96.2 $\mu\text{g}^*\text{h}/\text{mL}$ and (Cmax >21 $\mu\text{g}/\text{mL}$) for 500 mg QW dose

AUC variability (%CVb ¹)	Cmax Variability (%CVb ¹)	Any Participant (AUC >96.2 $\mu\text{g}^*\text{h}/\text{mL}$ or Cmax >21 $\mu\text{g}/\text{mL}$)
25	25	0

Note: 1, %CVb: between-participant coefficient of variation

Given the results in the tables above, it is unlikely that any subject exceeds the safety thresholds in the QD or QW MAD portions of the study.

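### The zero exceedances reported for 500 mg weekly (Protocol 9.5) cannot be right if the printed CV of 5 means 50; if 5 was run, the 50% case is missing

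*Protocol*

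**What the plan says.** The last part of Protocol 9.5 (Interim Analyses) describes simulations for the weekly cohort, Cohort 6. The event is "any participant having an 24 hour steady state AUC above log(96.2)" "or a Cmax above log(21) during the weekly MAD dosing portion of the study". The dose is expected to give an exposure that "will produce a steady state maximum daily AUC of 31.2" µg*h/mL. On the design it says "1000 simulated trials were produced for each value of %CVb (25, 35, 5)" and "Each simulated trial included 7 participants dosed at 500 mg". The result is "No simulated trial produced any participant who had either an AUC above log(96.2) or a Cmax above log (21)", and the section concludes that the risk of crossing a safety threshold is low.

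The paragraph before it, on 100 mg once daily, states "1000 simulated trials were produced for each value of %CVb (25, 35, and 50)". Tables 8 and 15 use the same three values, and the single-dose simulation treats 50% as its high-variability setting.

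Table 9 in section 4.3.4 gives the weekly result for one setting only, CV 25% for both AUC and Cmax, with probability 0. The text below it reads: "Given the results in the tables above, it is unlikely that any subject exceeds the safety thresholds in the QD or QW MAD portions".

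**The concern.** The third CV for the weekly simulation is printed as 5, where every parallel daily-dose display has 50. Either the list is truncated or a different, much smaller value was used. In the first case the stated result should be compatible with a CV of 50%, and it does not look so: the limit of 96.2 is only about three times the assumed AUC. In the second case the weekly cohort lacks the high-variability check that the daily cohorts received.

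The limit is the rat LOAEL exposure, which section 7.1.4 adopts as the MAD PK stopping criterion. The sentence is therefore a safety operating characteristic in a healthy-volunteer protocol. A reader of 9.5 and Table 9 sees how risk depends on variability for the daily doses and sees only zeros for the weekly dose.

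**Working it through.** **Inputs**
- Assumed AUC 31.2 µg*h/mL, limit 96.2, 7 active participants, 1000 trials per CV: Protocol 9.5.
- Log scale with normal error and no participant term: model [2] in Protocol 9.5.
- 31.2 taken as a median: Table 11 gives 31.3 and labels it a median. Protocol 9.5 does not say, so the arithmetic-mean reading is shown too.
- CV on the log scale: SAP 8.1.1.2 defines %CVb as 100 × sqrt(exp(SD²) − 1), so SD = sqrt(ln(1 + CV²)).

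**Formulas**
- p = 1 − Φ(ln(96.2/31.2)/SD), with ln(96.2/31.2) = 1.126
- any of 7 = 1 − (1 − p)^7
- chance of no exceedance in 1000 trials = (1 − any of 7)^1000

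**Results, 31.2 as median**

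| CV | SD | p per participant | any of 7 | expected trials per 1000 | chance of zero in 1000 |
|---|---|---|---|---|---|
| 5% | 0.050 | 0 | 0 | 0 | 1 |
| 25% | 0.246 | 0.0000024 | 0.0017% | 0.017 | 98% |
| 35% | 0.340 | 0.00046 | 0.32% | 3.2 | 3.9% |
| 50% | 0.472 | 0.0086 | 5.8% | 58 | 7 × 10⁻²⁷ |

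The reported zero is reproduced at CV 5% and 25%, is unlikely but possible at 35%, and is not reproduced at 50%. A direct simulation of 200,000 trials per CV gave 0.32% at CV 35% and 5.8% at CV 50%.

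**31.2 as arithmetic mean.** The median becomes 31.2/sqrt(1 + CV²). Any-of-7 is then 0.17% at CV 35% (chance of zero 18%) and 3.0% at CV 50% (chance of zero 4 × 10⁻¹⁴).

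**Cmax.** With the Table 11 median of 1.5 against a limit of 21, the any-of-7 probability at CV 50% is about 8 × 10⁻⁸. AUC alone drives the result.

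**Could another distribution explain the zero?** A normal distribution on the raw scale gives 0.01% of trials at CV 50%, which would make zero likely. It contradicts the log-scale model, and it gives 0.002 per participant for 100 mg daily at CV 50%, where Table 8 prints 0.028. The log-normal gives 0.031.

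**Cross-check within the protocol.** At CV 50% Table 8 prints a value below 0.001, but not 0, for 50 mg daily (median AUC 22.7 in Table 11), and 0.028 for 100 mg daily (median 39.8). The weekly AUC of 31.2 lies between these two. Against the same limit and CV its probability must lie between theirs, so it is not zero.

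**Scale of Table 8.** For 100 mg daily (39.8) at CV 25, 35 and 50% the log-normal gives 0.0002, 0.005 and 0.031 per participant, and 0.001, 0.033 and 0.197 for any of 7. Table 8 prints <0.001, 0.003 and 0.028. Its title speaks of any participant, but its values sit near the per-participant scale.

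**The case against.** A reader might infer that the protocol's own inputs give a 6% risk and that its zero is simply false. The documents do not support that. For the weekly simulation 50 is not printed; it is an inference, though a strong one. If 5 was run, the zero at that value is correct and the defect is an unexamined scenario. Nor does the CV 35% result contradict the text: three expected trials is an expectation, and none in 1000 can occur by chance.

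A reader might also infer that section 4.3.4 rests on this sentence. It cites Tables 8 and 9 instead, and the Table 9 zero at CV 25% is correct to any sensible rounding.

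The higher CVs are also stress cases. Table 11 gives the weekly AUC a median of 31.3 and an upper bound of 45.5. Under log-normality that implies a CV of about 23% if the bound belongs to a 90% interval (row label) or about 19% if it belongs to a 95% interval (footnote a). The Table 9 row therefore matches the protocol's own projection. Finally, escalation is decided by Bayesian predictions from observed data against 50%, together with safety review, and not by this advance simulation.

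All of this stands. It limits the consequence, but it does not explain a zero at CV 50% or supply the missing case.

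**Conclusion.** The concern holds in conditional form. If the printed 5 means 50, the reported result is incompatible with the stated inputs: about 5.8% of trials, or 3.0% with 31.2 as a mean, should contain an exceedance. If 5 was run, the weekly dose was not tested at the 50% variability applied to the daily doses. The text needs correction in both cases.

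The calculation assumes log-normal AUC, independent participants and the SAP's definition of CV. The choice between median and mean changes the size but not the conclusion at CV 50%.

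It does not follow that the weekly dose is unsafe or that the protocol's judgement of low risk is wrong. Even 6% is far below the 50% criterion, and no gate decision changes. This is a correction to a stated safety figure.

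**What to change.** 1. Confirm which CV values were run for the weekly simulation and whether 31.2 is a median or a mean.
2. Rerun at 25, 35 and 50%, and replace the statement that no trial showed an exceedance with the actual proportion at each CV.
3. Add the CV 35% and 50% rows to Table 9, taken from the sponsor's rerun and not from this review.
4. State in Tables 8 and 9 whether the probability is per participant or any of 7, and use the same scale in both. By our calculation the weekly AUC figures at CV 35% and 50% are about 0.05% and 0.9% per participant, or 0.3% and 6% for any of 7. Placing the any-of-7 figures beside Table 8 as printed would make the weekly dose look riskier at CV 50% than 100 mg daily (2.8%), although its assumed AUC is lower (31.2 against 39.8).

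The cost is a short simulation and a text and table edit. The printed weekly figures become slightly less favourable. No dose or stopping rule changes.
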